### 11.1.2 Study Safety Pauses

This study has no formal pause rules. However if during the weekly or expedited safety reviews the PSRT identifies safety concerns that warrant a safety pause, the PSRT will notify the sponsor. If a decision is made to pause the study, all enrollment will be held pending wider consultation with the PATH, funders and sponsor on whether to lift the pause or discontinued the study prematurely.

IVAC retains the right to temporarily suspend or prematurely discontinue this study at any time for matters related to safety. If the study is stopped or suspended prematurely, IVAC will inform the local principal investigator as well as regulatory authorities about the decision and the reasons for termination or suspension. If such action is taken, all efforts must be made to ensure the safety of the participants enrolled in the study. The principal investigator will assist IVAC in informing the responsible IEC and provide the reason for the suspension or termination. In case of premature study or study clinic closure, the monitor will conduct all activities as indicated in the close out monitoring visit.

## 11.2 Data Safety Monitoring Board

Given the wide global experience with seasonal influenza vaccines and the safety profile observed in the Phase 1 study, there will not be any Data Safety Monitoring Board (DSMB) for this study. The PSRT will be responsible for close safety oversight of the study.

## 12 Monitoring and Auditing

### 12.1 Monitoring Plan

Individuals qualified by education, training and experience will carefully monitor the study. The study monitors (from QuintilesIMS) will periodically contact the site and perform on-site visits. The extent, nature, and frequency of site visits will be based on such considerations as study

objectives, study design and complexity, and enrollment rate; periodicity and nature of monitoring activities will be described in the Monitoring Plan. The Monitoring Plan will detail reporting requirements to IVAC to keep it apprised of study progress. Representatives of IVAC or its designees may participate in monitoring visits or visit the study clinic on its own to provide proper oversight.

## **12.2 Set-up Visit (Site Initiation)**

The study monitor will contact the site prior to the start of the study to discuss the protocol and data collection procedures with site personnel. Prior to enrollment of participants at the study clinic, specific regulatory documents must be available, including approvals from the Vietnam Ministry of Health and from institutional review boards of the participating institutions. Curriculum vitae for key investigators must also be available. IVAC or CRO will inform the investigator of any additional documents that need to be provided.

## **12.3 Routine Monitoring Visits**

Monitoring will be conducted according to an agreed upon Monitoring Plan. The study may use a Risk Based Monitoring approach that will be targeted to issues most critical to the rights and welfare of study participants and the veracity and integrity of study data. The individuals responsible for monitoring the study will periodically review the progress of the study and should have access to all records necessary to ensure the ethical and safe conduct of the study and the integrity/validity of the recorded data.

During site visits and contacts, the monitor will:

1. Assess if consent was properly obtained
2. Assess adherence to the protocol eligibility criteria
3. Look for evidence that randomization was followed
4. Look for evidence that blinding was maintained
5. Check on study conduct and documentation of procedures/assessments related to the study endpoints:
  - Specimens obtained correctly
  - Specimens labeled correctly
6. Check on study conduct and documentation of protocol-required safety assessments, including SAEs
7. Ensure that there is documentation of withdrawals and deaths and reasons provided.

As part of study conduct, the Principal Investigator agrees to allow the monitor direct access to all relevant documents and to allocate his/her time and the time of his/her staff to the monitor to

discuss findings and any relevant issues. The study consent also makes participants aware that medical records relevant to events in the study may be accessed and viewed by people conducting and overseeing the study.

The Principal Investigator also agrees to allow representatives of IVAC or its designees to occasionally accompany the monitor during site visits.

#### **12.4 Close-out Visit**

Upon completion of the study, the study monitor and the investigator will conduct the following activities:

- Data clarification and/or resolution.
- Accounting, reconciliation and disposition of used and unused study products according to the instructions of the sponsor.
- Review of site study records for completeness.
- Ensure study data is handled according to instructions by IVAC.

#### **12.5 Audits and Inspections**

For the purpose of compliance with applicable regulatory guidelines IVAC or its designees or national regulatory authorities may conduct a site audit. This could occur at any time from site initiation to after conclusion of the study. If the national regulatory authority requests an inspection, the Principal Investigator must inform IVAC immediately about this request.

The Principal Investigator will allow the auditor direct access to all relevant documents and to allocate his/her time and the time of his/her staff to the auditor to discuss findings and any relevant issues.

### **13 Statistical Considerations**

#### **13.1 Study Hypothesis**

##### **Safety:**

A single dose of seasonal trivalent inactivated split virion influenza vaccine (IVACFLU-S) will be safe and well tolerated in adults 18 to 60 years of age.

##### **Immunogenicity:**

A single dose of IVACFLU-S seasonal trivalent split, inactivated influenza vaccine will induce immune responses to each of the three vaccine antigens to meet one or both age group specific Vietnam Ministry of Health licensure requirements.

### 13.2 Sample Size Considerations

This is a Phase 2/3 trial with primary objective to evaluate the safety and immunogenicity of one dose of IVACFLU-S. The sample size for this study was selected in response to MOH's requirement for additional safety data from Phase 2 before proceeding to Phase 3 and for primary safety and immunogenicity analysis to satisfy the MOH licensure requirement for influenza vaccine in adults from age 18 through 60. Total sample size for the Phase 2 is approximately 250 participants (at least 200 randomized to vaccine and 40 randomized to placebo). Phase 3 sample size is approximately 650 participants (at least 500 randomized to vaccine and 100 randomized to placebo). The two age groups (18 to 45, 46 to 60) will be equally distributed in both phases of the study. Block randomization will be stratified by site and age group. To account for potential drop-outs (expected to be low) and to address the challenge of stopping enrollment at a precise number due to the large sample size, sample size allows for an overage of approximately 5%. The sample size of this trial reflects guidance and endorsement by MOH at the MOH-IVAC Consultation Meeting held on 20 April 2016.

### 13.3 Safety

There will be 740 subjects randomized to IVACFLU-S arm in the phase 2/3 study; with account of 5% drop-out rate; there would be at least 700 evaluable participants for safety analysis. If no vaccine-related serious adverse events are observed in 700 vaccine recipients, study would be able to exclude events occurring at approximately 0.43% based on the upper bound of the one-sided 95% Confidence Interval (CI) using the Clopper-Pearson method. The probability of observing at least one vaccine-related serious adverse event in 700 subjects is 90% and >95% if the true rate of such events is 0.33% and 0.43% respectively. The precision of the estimate of AEs judged to be related to IVACFLU-S as bounded by 95% CI is presented in Table 16.

However, the full analysis population will be used for safety analysis, not the assumed number of 700 evaluable subjects.

**Table 16: Exact 95% Confidence Intervals around Potential Number of Study Related Adverse Events**

Sample size	Number of events	2-sided exact 95% CI
700	0	[0, 0.52*]
	1	[<0.01, 0.79]
	2	[0.03, 1.02]
	3	[0.08, 1.24]
	5	[0.23, 1.65]

\*one-sided, 97.5% CI

### 13.4 Immunogenicity

The Vietnam MOH guidance on serological immune response requirements [11] for influenza vaccine as summarized in Table 17 is a modification of the EMEA/CPMP serological criteria for assessing seasonal influenza for licensure [18].

**Table 17: Vietnam MOH Criteria for Evaluation of Influenza Vaccine Immune Responses**

	Age Group	
	18 – 45	46
Proportion achieving a HAI titer $\geq$ 1:40 (seroprotection)	$\geq$ 70%	$\geq$ 60%
Proportion achieving at least 4 fold rise in HAI titer (seroconversion)	$\geq$ 40%	$\geq$ 30%
GMT rise in HAI titer	$\geq$ 2.5 times	$\geq$ 2.0 times

Of the three criteria, seroconversion has been the most frequent criteria not meeting licensure threshold [19]. Though the study assumption is based on Phase 1 immunogenicity data for adults 18-45 years of age, we anticipate the immune response in those 46 - 60 will be comparable since significant decline in antibody response is most associated with those who are  $\geq$ 65 years of age [20]. Taken together with the immunogenicity results of the IVACFLU-S phase 1 study (section 2.1.6), the sample size consideration for immunogenicity for the study was based on the precision of the estimate of percent of vaccine recipients with HAI seroconversion and seroprotection responses. With a sample size of 100 evaluable vaccine recipients from each age group, the study provides the precision of immunogenicity response as estimated by width of 95% CI of  $\leq \pm 10.2\%$  around the range of estimated response rate (Table 18). An increase in sample size by 50% to 150 provides very limited statistical benefit as it only reduces the maximal width of 95% CI by 1.9% to  $\leq \pm 8.3\%$ . All power calculations were made using 10000 simulations of binomial responses to each strain, based on assumed true response rates and pass/fail criteria. All calculations were made using SAS version 9.3.

**Table 18: Observed Response Rate in 100 participants receiving study vaccine and Corresponding 95% CI**

Number of responder (%)	2-sided exact 95% CI
90 (90%)	[82.4%, 95.1%]
80 (80%)	[70.8%, 87.3%]
70 (70%)	[60.0%, 78.8%]
60 (60%)	[49.7%, 69.7%]

50 (50%)	[39.8%, 60.2%]
40 (40%)	[30.3%, 50.3%]
30 (30%)	[21.2%, 39.9%]

**13.4.1 Probability for demonstrating seroconversion criteria for licensure**

For the 18-45 year old cohort, if the true seroconversion response to each strain is  $\geq 49\%$ , then there is 91% probability that the point estimate for seroconversion to all three strains will be  $\geq 40\%$ . Likewise, if the true seroconversion response to each strain is  $\geq 60\%$ , then there is 92% probability that the lower bound of the exact 95% CI for seroconversion to all strains will be  $\geq 40\%$ . For the older age cohort (46-60 year old), if the true seroconversion response to each strain is  $\geq 39\%$ , then there is 93% probability that the point estimate for seroconversion to all three strains will be  $\geq 30\%$ . Given that the lowest seroconversion response in the IVAC Phase 1 trial was to B viral strain at 76.7% (95% CI, 57.7 90.1), there is high probability (Table 19) of demonstrating age group specific seroconversion requirement with a sample size of 100 evaluable participants per age group who received the study vaccine.

**Table 19: Probability of demonstrating seroconversion response to all 3 viral strains by age groups and assumed true response to each viral strain**

Age group (point estimate response)	True response		
	Probability > 90%	Probability > 95%	Probability > 99%
18-45 ( $\geq 40\%$ )	$\geq 49\%$	$\geq 51\%$	$\geq 54\%$
46- 60 ( $\geq 30\%$ )	$\geq 39\%$	$\geq 40\%$	$\geq 43\%$

**13.4.2 Probability for demonstrating seroprotection criteria for licensure**

For the 18-45 year old cohort there is 92% probability that the point estimate for seroprotection to all three strains will be  $\geq 70\%$  if the true response to each strain is  $\geq 78\%$ . Likewise if the true response to each strain is  $\geq 87\%$ , then there is 95% probability that the lower bound of the exact 95% CI for seroprotection to all strains will be  $\geq 70\%$ . In the older age cohort (46-60 year old), if the true seroprotection response to each strain is  $\geq 69\%$ , then there is 93% probability that the point estimate for seroprotection to all three strains will be  $\geq 60\%$ . Given that the lowest seroprotection response in the IVAC Phase 1 trial was to B viral strain at 93.3% (95% CI 77.9; 99.2), there is high probability (Table 20) of demonstrating age group specific seroprotection requirement with a sample size of 100 evaluable participants per age group who received the study vaccine.

**Table 20: Probability of demonstrating seroprotection response to all 3 viral strains by age groups and assumed true response to each viral strain**

Age group (point estimate response)	True response		
	Probability > 90%	Probability > 95%	Probability > 99%
18-45 ( $\geq 70\%$ )	$\geq 78\%$	$\geq 79\%$	$\geq 81\%$
46- 60 ( $\geq 60\%$ )	$\geq 69\%$	$\geq 70\%$	$\geq 72\%$

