### PROTOCOL SUMMARY

Title:	A Phase 2/3 Double Blinded, Randomized, Placebo-Controlled Study in Healthy Adult Volunteers in Vietnam to Examine the Safety and Immunogenicity of a Seasonal Trivalent Inactivated Split Virion Influenza Vaccine (IVACFLU-S) produced by IVAC
Description of Study Design:	
This is a phase 2/3, double-blind, placebo-controlled trial of 888 adults, ages 18 to 60 years old randomized to receive vaccine or placebo according to schema below. Phase 2 will be conducted at 1 site of Long An (252 subjects). Following a determination of safety of vaccine in phase 2 study by Protocol Safety Review Team (PSRT) review and with approval from Vietnam Ministry of Health (MOH), Phase 3 enrollment will commence at 2 sites, Long An (252 subjects, including 210 vaccine recipients and 42 placebo recipients) and Dong Nai (384 subjects, including 320 vaccine recipients and 64 placebo recipients).
 
Safety will be assessed in all Phase 2 and 3 participants through Day 91. Safety data till Day 8 post-vaccination from the phase 2 study will be presented to Protocol Safety Review Team (PSRT) for evaluation and an interim report will be filed with local institutional review board (IRB) and MOH. Immunogenicity will be assessed only in Phase 3 participants. Blood samples will be collected in a subset of 252 individuals (210 vaccine recipients and 42 placebo recipients) randomized at one of the study sites to get evaluable samples from at least 200 vaccine recipients (100 each from both age groups) and 40 placebo recipients (20 each from both age groups) 21 days after vaccination.
 
Approximate participant distribution based on age, study arm and study will be as follows:

Study Hypothesis:	Age group	IVACFLU-S	Placebo	Total	
	Phase 2				
	18 - 45	105	21	126	
	46 - 60	105	21	126	
	Phase 3				
	18 - 45	265	53	318	
	46 - 60	265	53	318	
	Safety:				
	A single dose of seasonal trivalent inactivated split virion influenza vaccine (IVACFLU-S) will be safe and well tolerated in adults 18 to 60 years of age.				
	Immunogenicity:				
	A single dose of seasonal trivalent inactivated split virion influenza vaccine (IVACFLU-S) will induce immune responses to each of the three vaccine antigens to meet one or both age group specific Vietnam Ministry of Health (MOH) licensure requirements.				
		Criteria	18 – 45 year old	46 – 60 year old	
	Seroprotection (HAI $\geq 1:40$ )	$\geq 70\%$	$\geq 60\%$		

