**Table 15: Schema for randomization**

Age group	IVACFLU-S	Placebo	Total
Phase 2			
18 - 45	105	21	126
46 - 60	105	21	126
Phase 3			
18 - 45	265	53	318
46 - 60	265	53	318

Figure 1: Enrollment and schedule of trial activities

[figure not shown]

Total study participation duration for one participant: about 91 days

[figure not shown]
\*At Ben Luc site in phase 3, sera samples will be collected prior to vaccination on S1/D1 and D22

Figure 2: Summary of study design

Phase 2:

Phase 3:

Safety will be assessed in all Phase 2 and 3 participants through Day 91. Immunogenicity will be assessed only in Phase 3 participants. Blood samples will be collected at Day 1 before vaccination in a subset of 252 individuals randomized at one of the study sites to get evaluable samples from at least 200 vaccine recipients (100 each from both age groups) and 40 placebo recipients (20 each from both age groups) and 21 days after vaccination.

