### 16.1.1 PROBABILITY FOR DEMONSTRATING SEROCONVERSION CRITERIA FOR LICENSURE

For the 18-45 year old cohort, if the true seroconversion response to each strain is  $\geq 49\%$ , then there is 91% probability that the point estimate for seroconversion to all three strains will be  $\geq 40\%$ .

Likewise, if the true seroconversion response to each strain is  $\geq 60\%$ , then there is 92% probability that the lower bound of the exact 95% CI for seroconversion to all strains will be  $\geq 40\%$ . For the older age cohort (46-60 years old), if the true seroconversion response to each strain is  $\geq 39\%$ , then there is 93% probability that the point estimate for seroconversion to all three strains will be  $\geq 30\%$ . Given that the lowest seroconversion response in the IVAC Phase 1 trial was to B viral strain at 76.7% (95% CI, 57.7-90.1), there is high probability (Table 5) of demonstrating age group specific seroconversion requirement with a sample size of 100 evaluable participants per age group who received the study vaccine.

Table 5: Probability of demonstrating seroconversion response to all 3 viral strains by age groups and assumed true response to each viral strain.

Age group (point estimate response)	True response		
	Probability > 90%	Probability > 95%	Probability > 99%
18-45 ( $\geq 40\%$ )	$\geq 49\%$	$\geq 51\%$	$\geq 54\%$
46- 60 ( $\geq 30\%$ )	$\geq 39\%$	$\geq 40\%$	$\geq 43\%$

Document: \\EEDC-NAS01A\Biosdata\Path\IVACFLU-S\IYA06804\Biostatistics  
Documentation\SAP\IVACFLU-S-0203\_SAP\_Draft v1.0

Author: [name]

Version Number:

1.0

Version Date:

[11AUG2017]

Template No: CS\_TP\_BS016 Revision 4  
Effective Date: 01Apr2016

Reference: CS\_WI\_BS005

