## 16.1.2 PROBABILITY FOR DEMONSTRATING SEROPROTECTION CRITERIA FOR LICENSURE

For the 18-45 year old cohort there is 92% probability that the point estimate for seroprotection to all three strains will be  $\geq 70\%$  if the true response to each strain is  $\geq 78\%$ . Likewise if the true response to each strain is  $\geq 87\%$ , then there is 95% probability that the lower bound of the exact 95% CI for seroprotection to all strains will be  $\geq 70\%$ . In the older age cohort (46-60 years old), if the true seroprotection response to each strain is  $\geq 69\%$ , then there is 93% probability that the point estimate for seroprotection to all three strains will be  $\geq 60\%$ . Given that the lowest seroprotection response in the IVAC Phase 1 trial was to B viral strain at 93.3% (95% CI 77.9; 99.2), there is high probability (Table 6) of demonstrating age group specific seroprotection requirement with a sample size of 100 evaluable participants per age group who received the study vaccine.

Table 6: Probability of demonstrating seroprotection response to all 3 viral strains by age groups and assumed true response to each viral strain.

Age group (point estimate response)	True response		
	Probability > 90%	Probability > 95%	Probability > 99%
18-45 ( $\geq 70\%$ )	$\geq 78\%$	$\geq 79\%$	$\geq 81\%$
46- 60 ( $\geq 60\%$ )	$\geq 69\%$	$\geq 70\%$	$\geq 72\%$

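### Pass probabilities in Protocol Tables 19–20 (SAP Tables 5–6) are given only at 100 evaluable, a locally favourable size; one text figure is off by a point, and four of twelve cells fall slightly short under random 5% loss

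*Combined protocol and SAP*

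**What the plan says.** Protocol 13.4 sets the basis: "With a sample size of 100 evaluable vaccine recipients from each age group". Section 13.4 also says the power figures come from 10,000 binomial simulations per strain, and 13.8 says licensure is judged on the point estimate. Two tables then list the true rates at which all three strains pass with probability above 90%, 95% and 99%:

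- Seroconversion: "Table 19: Probability of demonstrating seroconversion response to all 3 viral strains by age groups and assumed true response to each viral strain". Entries are 49/51/54% for ages 18–45 (threshold 40%) and 39/40/43% for ages 46–60 (threshold 30%).
- Seroprotection: "Table 20: Probability of demonstrating seroprotection response to all 3 viral strains by age groups and assumed true response to each viral strain". Entries are 78/79/81% for ages 18–45 (threshold 70%) and 69/70/72% for ages 46–60 (threshold 60%).

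The text gives 91% at a true 49% and 93% at a true 39% for seroconversion, and 93% at a true 69% for seroprotection. For ages 18–45 at a true 78% it says "there is 92% probability that the point estimate for seroprotection to all three strains will be" at or above the 70% threshold. SAP 16.1.1 and 16.1.2 repeat all of this ("Table 5: Probability of demonstrating seroconversion response to all 3 viral strains by age groups and assumed true response to each viral strain" and "Table 6: Probability of demonstrating seroprotection response to all 3 viral strains by age groups and assumed true response to each viral strain").

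The sampled subset is "Long An (252 subjects, including 210 vaccine recipients and 42 placebo recipients", that is 105 vaccine recipients per age group. Protocol 4.1 allows for 5% dropout, and the aim is "to get evaluable samples from at least 200 vaccine recipients (100 each from both age groups".

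**The concern.** A point-estimate rule is a rule on counts: each strain needs at least the threshold times n, rounded up to a whole responder. At n = 100 nothing is rounded up. At most neighbouring sizes at least one threshold is, and the pass probability drops. With 105 vaccinated per age group and 5% loss, the expected evaluable number is 99.75, so the design lands around 100 rather than on it. The tables show no other size and do not mention the effect.

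At stake is the accuracy of the pass probabilities that support the primary immunogenicity objective. If they do not reproduce, or are not what the enrolled design delivers, a reader will credit the trial with a slightly different power from the one it has.

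**Working it through.** **Inputs.** Thresholds: Protocol Table 17. True rates and target levels: Tables 19 and 20. Evaluable n = 100: 13.4. Bled subset: 210 vaccine recipients (Protocol Summary), divided equally by age, so 105 each. Loss: 5% (4.1). Strains are independent, as the per-strain simulation implies.

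**Formula.** P(pass) = [P(X ≥ k)]³, with X ~ Binomial(n, p) and k = threshold × n rounded up.

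**Step 1: the plan's figures at n = 100** (k = 40, 30, 70, 60).

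| Group | True rates | Exact P(pass) |
|---|---|---|
| Seroconversion 18–45 | 49 / 51 / 54% | 91.75 / 96.87 / 99.45% |
| Seroconversion 46–60 | 39 / 40 / 43% | 92.93 / 95.63 / 99.17% |
| Seroprotection 18–45 | 78 / 79 / 81% | 93.21 / 96.35 / 99.18% |
| Seroprotection 46–60 | 69 / 70 / 72% | 93.60 / 96.30 / 98.96% |

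Eleven of the twelve cells are met. The 72% cell is 0.04 points short; the simulation standard error there is √(0.9896 × 0.0104 / 10,000) = 0.10 points. At a true 73% the value is 99.49%.

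The lower-bound statements also reproduce. The Clopper-Pearson lower limit reaches 40% at 51 of 100 and 70% at 80 of 100, giving 92.1% at a true 60% (stated 92%) and 94.9% at a true 87% (stated 95%).

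**Step 2: the 92% figure.** For 78%: P(X ≥ 70) = 0.97684, and 0.97684³ = 0.9321. The simulation standard error is √(0.9321 × 0.0679 / 10,000) = 0.25 points.

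- Measured from 92.0%, the gap is 1.21 points, or 4.8 standard errors.
- If the text rounds to the nearest percent, the simulated value was below 92.5%, still 0.71 points or 2.8 standard errors away.
- If the text truncates, a simulated value just under 93.0% would be within one standard error.

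Either convention puts the exact value at 93%. A strict greater-than rule gives 88.9%, so it does not explain 92%.

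**Step 3: dependence on n.** Number of the twelve cells below their stated level:

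| n | 95 | 96 | 97 | 98 | 99 | 100 | 101 | 102 | 103 | 104 | 105 |
|---|---|---|---|---|---|---|---|---|---|---|---|
| cells | 5 | 8 | 5 | 5 | 7 | 1 | 4 | 4 | 4 | 3 | 0 |

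**Step 4: the design as enrolled.** Let N ~ Binomial(105, 0.95). The mean is 105 × 0.95 = 99.75, P(N = 100) = 17.9% and P(N ≥ 100) = 57.1%. Averaging P(pass) over N, four cells miss their level:

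| Cell | Stated | Averaged | Shortfall (points) | Next whole percent |
|---|---|---|---|---|
| Seroconversion 46–60, 40% | >95% | 94.49% | 0.51 | 41%: 96.65% |
| Seroconversion 46–60, 43% | >99% | 98.89% | 0.11 | 44%: 99.39% |
| Seroprotection 18–45, 81% | >99% | 98.88% | 0.12 | 82%: 99.52% |
| Seroprotection 46–60, 72% | >99% | 98.63% | 0.37 | 73%: 99.32% |

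The four text probabilities become 90.06% (49%), 91.27% (39%), 91.52% (78%) and 92.16% (69%).

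**The case against.** The plan says openly that its figures are for 100 evaluable per age group, and it treats 100 as a minimum. Quoting power at the target number is normal practice, and averaging over a random number is a refinement. The 0.04-point miss in the 72% cell could easily come from a correct simulation. The 92% figure errs on the cautious side. Protocol 13.2 and 5.4.5 expect losses to be low, and 13.2 says the overage also covers difficulty in stopping enrolment at a precise number, so the 5% loss model is one choice among several. All of this stands, and it limits the weight of the point.

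Three stronger readings are tempting, and the documents support none of them.

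- **The tables hold only at exactly 100.** They do not depend on that size: all twelve cells are met at 105, and the 18–45 seroconversion cells at 51% and 54% are met at every size from 95 to 106.
- **Four cells fail whatever the loss.** The count depends on the loss model. A fixed 99 gives seven and full retention gives none. With 2% random loss the 43% cell reaches 99.01%; with 1% the 81% cell reaches 99.01%.
- **These are the plan's only power figures.** The same sections give the two lower-bound probabilities, and 13.4 rests the immunogenicity sample size on precision.

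The objection does not remove two facts: 93% is the exact figure at a true 78%, and the plan's own 105 with 5% loss has an expected evaluable number just under 100.

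**Conclusion.** The point holds, and it is small. At n = 100 one text probability should read 93% instead of 92%. That understates power, by more than simulation error if the text rounds to the nearest percent. One table cell should read 73% instead of 72% on an exact calculation, although that miss is within simulation error. For the design as enrolled, four of twelve cells fall short by 0.11 to 0.51 points, and each affected true rate moves up by one percentage point. These averaged results assume independent strains, an equal split by age and random 5% loss from 105. Per-protocol exclusions beyond dropout are not modelled.

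The sample-size conclusion is unaffected. At the lowest Phase 1 rates (76.7% seroconversion, 93.3% seroprotection), the averaged pass probability exceeds 99.999% for every criterion. At the lower confidence limits of those rates (57.7% and 77.9%) it is at least 91%.

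**What to change.** Recompute Protocol Tables 19 and 20, SAP Tables 5 and 6 and the accompanying text by exact binomial in place of simulation.

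1. At n = 100, change 92% to 93% (18–45 seroprotection, true 78%) and change the 72% cell to 73%.
2. Add, as the figures for the design as enrolled, the values under random 5% loss from 105: text probabilities of 90%, 91%, 92% and 92% (true 49%, 39%, 78% and 69%), and cells of 41% and 44% (46–60 seroconversion), 82% (18–45 seroprotection) and 73% (46–60 seroprotection) in place of 40%, 43%, 81% and 72%.
3. State the loss assumption, and add a sentence saying that the pass probability moves up and down with n because the rule is a whole count.

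The cost is a few lines of code and some wording in Protocol 13.4 and SAP 16.1. The sample size, endpoints, analyses and decision rule do not change.
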